12.5.3 Physical Examination and Adverse Events

Physical examination results will be summarized by frequency of presence of abnormalities in body system (beyond the DMD diagnosis) and in particular any changes in the physical examination over time.

TEAEs will be summarized. Coding will be done by system organ class and preferred term (using MedDRA). Level of severity will be assessed using the CTCAE grading system.

Summaries will include:

- Summaries at the patient level
 - How many patients had any TEAE, any SAE, highest severity of TEAE within a patient across all infusions, highest relationship level of TEAE within a patient across all infusions, highest intervention level regarding IP (e.g., discontinued versus reduced dose versus temporarily stopped versus no interruption in infusions), and worst outcome within a patient (e.g., AE did not resolve and has a permanent effect).
- Summary at the event level
 - Summaries will be done using MedDRA coding by events and overall, summarizing by system organ class and preferred term, by relationship to IP, severity, intervention, and outcome.

Listing tables will be provided for all AEs.

12.5.4 Concomitant Medications and/or Other Treatments

GCs will be summarized by type of GC (prednisone versus deflazacort), by schedule (daily versus any other), and by treatment. Patients are required not to change the GC dose while on study, if possible. Any changes in doses or schedule will be listed.

Other concomitant medications will be summarized by Anatomic Therapeutic Chemical classification class and preferred term. Each medication will be counted once within a patient using it, regardless of the number of times it was reported on the eCRFs. The summaries will note new medications or supplements versus those already given at baseline and study entry. Any other treatment or surgeries will be listed and described; however, those are expected to be few, without a need to be summarized using tables.

12.6 Efficacy Assessments

12.6.1 Secondary Objective

The secondary objective is to compare the efficacy of viltolarsen administered IV at weekly doses of 80 mg/kg over a 48-week Treatment Period versus natural history controls in ambulant and non-ambulant boys ≥ 8 years of age with DMD for the following endpoints: absolute and percent predicted PEF, FVC, and FEV1, Brooke and Vignos functional scales, and the NSAA. The PUL and hand-held dynamometry will be described and the change over time estimated for the viltolarsen-treated group only.

In addition to the comparison methods described below, all outcomes for both the viltolarsen-treated and historical control groups will be summarized and tabulated at each time point assessed. Time points in the historical control will match those of the viltolarsen-treated group within pre-defined tolerances. Outcomes at baseline will be compared between viltolarsen and control groups using methods appropriate for the distribution of each outcome.

12.6.1.1 Peak Expiratory Flow

The change in both absolute and percent predicted PEF rate over the length of the study will be compared between patients receiving viltolarsen and the historical control group using mixed models with repeated measures. These models allow the use of all available assessments per patient, will include a random term per individual, and will assess the additional predictive value of a random slope term. Covariates of age and baseline value will be included. Steroid exposure

will be evaluated and included as an additional covariate if necessary. The pulmonary outcome will be the dependent variable, time and treatment group will be the independent variables, and a time by treatment group interaction will be included if appropriate. Percent predicted values will be calculated from absolute values using equations based on age, height, and ethnicity (see SRM for details).

12.6.1.2 Forced Vital Capacity

The change in absolute and percent predicted FVC will use the same methods described above for percent predicted PEF rate.

12.6.1.3 Forced Expiratory Volume in 1 Second

The change in absolute and percent predicted FEV1 will use the same methods described above for percent predicted PEF rate.

12.6.1.4 Brooke and Vignos Scales

Brooke scale: The change in the Brooke function scale over the length of the study will be compared between patients receiving viltolarsen and the historical control group using mixed models with repeated measures. These models allow the use of all available assessments per patient, will include a random term per individual, and will assess the additional predictive value of a random slope term. These models also have the flexibility to adequately model the quasi-continuous nature of the Brooke functional scale. The pulmonary outcome will be the dependent variable, time and treatment group will be the independent variables, and a time by treatment group interaction will be included if appropriate. Covariates of age and baseline value will be included and steroid exposure will be evaluated and included as an additional covariate if necessary.

Vignos scale: The change in the Vignos functional scale will use the same methods described above for the Brooke functional scale.

12.6.1.5 Muscle Strength Outcomes (Hand-held Dynamometry)

The change over time in hand-held dynamometry values will be estimated in patients receiving viltolarsen using a mixed model with repeated measures. As the historical control group does not contain hand-held dynamometry assessments, no comparisons between viltolarsen and

control will be performed. Here a separate model will be performed for each muscle. Hand-held dynamometry values will act as the dependent variable, time will be the independent variable, and a random term for individual will be included. Covariates of age and baseline value will be included and steroid exposure will be evaluated and included as an additional covariate if necessary.

12.6.1.6 Performance of Upper Limb

The change over time in the PUL will be estimated in patients receiving viltolarsen using a mixed model with repeated measures. As the historical control group does not contain PUL assessments, no comparisons between viltolarsen and control will be performed. PUL values will act as the dependent variable, time will be the independent variable, and a random term for individual will be included. Covariates of age and baseline value will be included and steroid exposure will be evaluated and included as an additional covariate if necessary.

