Clinical Efficacy Measures	
The following assessments will be performed:
 
 • PEF • FVC • FEV1 • PUL • Brooke scale • Vignos scale • Hand-held dynamometer (elbow extension, elbow flexion, knee extension, and knee flexion on the dominant side only) • NSAA
Exploratory Measures	
 • TSQM • PODCI • PARS III Questionnaire • PCF • Actigraphy • Loss of ambulation
Pharmacokinetic Measures	
Viltolarsen levels in plasma will be assessed at time points for each patient in which anti-viltolarsen antibody is detected.

Statistical Methods	
Sample Size: The target sample size is 20 patients. A minimum of 8 ambulant patients will be enrolled.
 
Assuming a sample size of 20, at least 1 adverse drug reaction with an incidence of 15% may be detected at a probability of $\geq 95\%$ for the safety profile, which is the primary outcome. Based on this, it was decided that 20 patients should be enrolled to confirm safety.
 
Analysis Populations: The Safety Population will consist of all patients who received at least 1 dose of IP. This will be the primary analysis population for the evaluation of safety. The modified Intent-to-Treat Population will consist of all patients who received at least 1 dose of IP and have a baseline assessment and at least 1 post-baseline efficacy assessment. This will be the analysis population for the evaluation of efficacy.

	
General Statistical Considerations: All measurements will be analyzed based upon the type of distribution, and descriptive statistics will be presented by time point, as appropriate.
 
Primary Safety Evaluation: Safety analyses will be performed using the Safety Population. TEAEs will be summarized by system organ class and preferred term (using the Medical Dictionary for Regulatory Activities), by relationship to IP, and by intensity (Common Terminology Criteria for Adverse Events grade).
 
Pharmacokinetic Evaluation: Population pharmacokinetic analyses will be presented in a separate report.

--	--

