2.1.3 Rationale for Study Design and Control Group

For the comparator to assess the secondary endpoint, the natural history group is referred. Although the sponsor understands the complexity in interpreting an open-label study with a natural history, external comparator control group due to the heterogeneity of the disease progression in DMD, an open-label historical control study was designed to account for beneficence, ethics, and the inherent difficulty to enroll a placebo-controlled study after an accelerated approval is granted in the United States (US).

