12.6.2.2 Pediatric Outcome Data Collection Instrument

Descriptive statistics of the PODCI will be generated at each time point the questionnaire is administered for global function and each of the sub-scores: upper extremity functioning, transfers and basic mobility, sports and physical function, comfort/pain, and happiness with physical condition. The change over time in scores will be estimated in patients receiving viltolarsen using a mixed model with repeated measures. Here a separate model will be performed for each score or sub-score. Score values will act as the dependent variable, time will be the independent variable, and a random term for individual will be included. This will allow exploration of the change, if any, in sub-scores in response to viltolarsen treatment.

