12.6.2.4 Peak Cough Flow

Descriptive statistics of PCF will be generated at each time point the assessment is performed. The change over time in scores will be estimated in patients receiving viltolarsen using a mixed model with repeated measures. PCF values will act as the dependent variable, time will be the independent variable, and a random term for individual will be included. This will allow exploration of the change, if any, in PCF in response to viltolarsen treatment.

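### The single-arm change-over-time models name one random term per boy and no random slope, so standard errors for a linear slope or for late change are too small if boys decline at different rates

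*Combined protocol and SAP*

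**What the plan says.** Five sections of the protocol describe single-arm repeated-measures models in nearly the same words.

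- PUL (12.6.1.6): "time will be the independent variable, and a random term for individual will be included".
- Hand-held dynamometry (12.6.1.5), one model per muscle: "Hand-held dynamometry values will act as the dependent variable, time will be the independent variable, and a random term for individual will be included".
- PODCI (12.6.2.2), with matching text for PARS III (12.6.2.3): "Score values will act as the dependent variable, time will be the independent variable, and a random term for individual will be included".
- PCF (12.6.2.4): "PCF values will act as the dependent variable, time will be the independent variable, and a random term for individual will be included".

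None of them names a random slope, a residual covariance structure or a robust standard error, or says whether time is continuous or categorical. PUL and dynamometry add age and baseline as covariates.

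The PEF model (12.6.1.1), which FVC and FEV1 follow, goes further: it "will include a random term per individual, and will assess the additional predictive value of a random slope term". Section 12.6.1.4 does the same for Brooke, and Vignos follows it. The NSAA model (12.6.1.7) names no random term at all.

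Section 2.1.3 says that an externally controlled study is complex to interpret "due to the heterogeneity of the disease progression in DMD". Section 12.1 leaves further detail to a SAP that overrides the protocol where they differ.

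**The concern.** In Sections 12.6.1.1 and 12.6.1.4 the slope is listed as something extra to the individual term. The natural reading of the single-arm sections, which have only the individual term, is therefore a random intercept. That model gives every boy the same rate of change. The trial enrols ambulant and non-ambulant boys from 8 years with no upper age limit, on or off glucocorticoids, and the sponsor itself expects progression to vary.

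When rates do vary, a random-intercept fit treats the spread of slopes as independent visit-level noise and averages it down over all visits. The information on the mean slope really comes from only 20 boys. The standard error is then too small, as is any interval or p-value built on it. PUL and dynamometry are secondary endpoints without a control comparison, so the precision of the estimated change carries much of their interpretation. Too small a standard error could make an inconclusive result look like demonstrated stability or change.

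**Working it through.** **The plan's own figure.** Section 12.2 gives the only sample-size figure: at least 95% probability of seeing a reaction of 15% incidence in 20 patients. 1 − 0.85^20 = 0.961, so it reproduces. It has no bearing on the precision of these models, for which no figure is stated.

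**Inputs.** N = 20 (Synopsis: "The target sample size is 20 patients"). Post-baseline visits are Weeks 13, 25, 37 and 49 (Tables 1 and 2). If baseline is only a covariate, T = 4 responses; if it is also a response, T = 5 with week 0 added. The slope SD τ and residual SD σ are not in the documents. I write k for the slope SD per 48 weeks divided by σ and vary it from 0.5 to 4.

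**Formulas** (balanced data, linear time):

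- Sxx = Σ(t − mean t)². For T = 4: 324 + 36 + 36 + 324 = 720. For T = 5: 1488.8.
- λ = τ²·Sxx/σ² = k²·Sxx/48², that is 0.3125k² (T = 4) or 0.646k² (T = 5).
- True variance of the mean slope: σ²(1 + λ)/(N·Sxx).
- Expected variance reported by the random-intercept fit: σ²(1 + λ·(N−1)/(N(T−1)−1))/(N·Sxx). The multiplier of λ is 19/59 = 0.322 (T = 4) or 19/79 = 0.241 (T = 5).
- Reported SE / true SE = the square root of the ratio of the last two lines.

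Example, T = 4, k = 2: λ = 1.25, and the ratio is √[(1 + 0.322 × 1.25)/2.25] = √0.623 = 0.79.

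| k | SE ratio, T = 4 | Coverage, T = 4 | SE ratio, T = 5 | Coverage, T = 5 |
|---|---|---|---|---|
| 0.5 | 0.98 | about 94% | 0.95 | about 94% |
| 1 | 0.92 | 93% | 0.84 | 90% |
| 2 | 0.79 | 88% | 0.67 | 81% |
| 3 | 0.71 | 83% | 0.59 | 76% |
| 4 | 0.66 | 80% | 0.55 | 72% |

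Coverage is for nominal 95% intervals in simulated trials of 20 boys. Per-patient slopes, which match a random-slope model in balanced data, gave about 95% throughout.

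**With covariates.** In 150 REML fits per setting with age and baseline included (T = 4), coverage was 88% for random intercept against 94% for random slope at λ = 1 (k = 1.8), and 83% against 95% at λ = 4 (k = 3.6).

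**Categorical time, random intercept only (T = 5).** Coverage of change from baseline at Weeks 13, 25, 37 and 49 is about 96%, 95%, 94% and 91% at k = 1. At λ = 2 (k = 1.8) it is 98%, 96%, 92% and 86%. The shortfall is confined to late visits.

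**Models affected.** Secondary: dynamometry 4 (two elbow and two knee movements, Section 9.16.1.1) + PUL 1 = 5. Exploratory: PODCI 6 (global and five sub-scores) + PARS III 7 (total and six sub-scales) + PCF 1 = 14. TSQM has two time points; with T = 2 the multiplier of λ is 19/19 = 1, so nothing is lost.

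**The case against.** The text does not say intercept only. It asks for a mixed model with repeated measures, which leaves room for a structured residual covariance, and the SAP may settle the matter. This stands in part: intercept-only is an inference, though one drawn from the plan's own usage, and no SAP text supplied here changes it. A reader might infer that the plan rules out a random slope; it does not.

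A reader might also infer that all intervals for change will be too narrow. The documents do not support that. Section 12 states no interval, test or decision rule for these endpoints, the coding of time is open, and with categorical time the early contrasts are sound or slightly conservative. If slopes vary little (k = 0.5), the loss is negligible even with linear time.

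Nor is the model estimate the only result for PUL and dynamometry: Section 12.6.1 also tabulates every outcome at each visit, and those summaries do not depend on the random-effects structure. It would likewise be wrong to say that all comparative models consider a slope, since NSAA names no random term and the others only assess one. Finally, 14 of the 19 models are exploratory, and the remark on heterogeneity in Section 2.1.3 concerns disease progression, not psychosocial scores.

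**Conclusion.** The point holds with conditions. If the single-arm models are fitted with a random intercept only and boys change at different rates, the standard error is too small for a linear time slope and, with categorical time, for late change such as Week 49. The direction follows from the model; the size cannot be fixed from the documents. Over the assumed range the effect runs from trivial (about 94% coverage at k = 0.5) through moderate (90–93% at k = 1, 81–88% at k = 2) to large (72–80% at k = 4). These figures assume linear change, complete balanced visits and 20 boys. The consequence is greatest for the five secondary models. The primary safety objective and the sample size are unaffected. It should be corrected before the SAP is final.

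**What to change.** In Sections 12.6.1.5, 12.6.1.6 and 12.6.2.2 to 12.6.2.4, or in the SAP:

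- State whether time is continuous or categorical.
- With continuous time, fit a random intercept and a random slope. With categorical time, fit an unstructured covariance over the post-baseline visits.
- Use Kenward-Roger degrees of freedom.
- If the model does not converge, use each patient's slope (or change) with a one-sample t interval.
- Align the NSAA model in Section 12.6.1.7, which names no random term.

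The cost is about one sentence per model. Intervals will be somewhat wider. Non-convergence is possible with 20 patients, since an unstructured matrix over four visits has 4 × 5/2 = 10 parameters; the fallback covers it.

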12.6.1.7 North Star Ambulatory Assessment

NSAA will be compared between patients receiving viltolarsen and the historical control group using mixed models with repeated measures. Covariates of age and baseline value will be included. Steroid exposure will be evaluated and included as an additional covariate if necessary.

12.6.1.8 Analyses Comparing NS-065/NCNP-01 Patients to Historical Controls

A matched data set from the CINRG DNHS data will be created. The purpose of the matching is to create a group data set that corresponds in characteristics to the patients in this study. The CINRG DNHS data set includes patients from 2 years old to over 30 years old, some of whom have been followed for close to a decade. Therefore, it is important to create a comparator group which will allow valid group comparisons. No patient-to-patient matched analysis is proposed. The sole purpose of the matching is to create a historical control group which is comparable in its basic characteristics to the study patient group. The final CINRG DNHS data set is expected to have between 16 and 32 patients included with time intervals of evaluations between 6 and 15 months.

12.6.2 Exploratory Objectives

12.6.2.1 Treatment Satisfaction Questionnaire

Descriptive statistics of the TSQM will be generated at each time point the questionnaire is administered for each of the 4 sub-scores: effectiveness, side effects, convenience, and global satisfaction. The change over time in scores will be estimated in patients receiving viltolarsen using a mixed model with repeated measures. Here a separate model will be performed for each sub-score. Sub-score values will act as the dependent variable, time will be the independent variable, and a random term for individual will be included. This will allow exploration of the change, if any, in sub-scores in response to viltolarsen treatment.

12.6.2.2 Pediatric Outcome Data Collection Instrument

Descriptive statistics of the PODCI will be generated at each time point the questionnaire is administered for global function and each of the sub-scores: upper extremity functioning, transfers and basic mobility, sports and physical function, comfort/pain, and happiness with physical condition. The change over time in scores will be estimated in patients receiving viltolarsen using a mixed model with repeated measures. Here a separate model will be performed for each score or sub-score. Score values will act as the dependent variable, time will be the independent variable, and a random term for individual will be included. This will allow exploration of the change, if any, in sub-scores in response to viltolarsen treatment.

12.6.2.3 Personal Adjustment and Role Skills Scale, 3rd Edition Questionnaire

Descriptive statistics of the PARS III Questionnaire will be generated at each time point the questionnaire is administered for total score and each of the 6 sub-scales: peer relations, dependency, hostility, productivity, anxiety/depression, and withdrawal. The change over time in scores will be estimated in patients receiving viltolarsen using a mixed model with repeated measures. Here a separate model will be performed for each score or sub-score. Score values will act as the dependent variable, time will be the independent variable, and a random term for individual will be included. This will allow exploration of the change, if any, in sub-scores in response to viltolarsen treatment.

12.6.2.4 Peak Cough Flow

Descriptive statistics of PCF will be generated at each time point the assessment is performed. The change over time in scores will be estimated in patients receiving viltolarsen using a mixed model with repeated measures. PCF values will act as the dependent variable, time will be the independent variable, and a random term for individual will be included. This will allow exploration of the change, if any, in PCF in response to viltolarsen treatment.

12.6.2.5 ActiGraph GT9x

Validity will be explored through correlation of all clinical strength and function tests and patient reported outcomes with raw data obtained from the AGT9x during clinical testing. Information such as steps, speed, body position/location (using vector magnitude per minute data) will be derived from the raw data; relationships with clinical tests will result from data conversions, descriptive analysis, and correlations with the raw data. Additionally, raw data will be analyzed throughout the study to explore changes in activity and sleep-wake patterns. Throughout the full study, 2-week bouts of continuous data will be analyzed through R*Studio (version 3.5.1, Vienna, Austria) and the nparACT package (version 0.8) to determine sleep-wake rhythms. Sleep-wake rhythms are measured as intradaily variability (quantifies the frequency and extent of transitions between periods of rest and activity on an hourly basis) and relative amplitude (derived from the normalized difference between the most active 10-hour period and least active 5-hour period in an average 24-hour pattern). Raw data will also be analyzed with ActiLife software to identify and score sleep periods defined as nightly percent sleep efficiency (total time in bed/total time asleep), average number of nightly awakenings (mean number of nightly awakenings longer than 3-minute durations), and average duration of nightly awakenings (mean duration of nightly awakenings that are longer than 3 minutes). Effect sizes to determine the magnitude of differences in change over time will be computed.

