6 STUDY POPULATION SELECTION

6.1 Study Population

A target sample size of 20 patients (ambulant and non-ambulant boys, ≥ 8 years of age; a minimum of 8 ambulant patients will be enrolled) with DMD who meet the eligibility criteria below will be enrolled.

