9.18.4 Other Assessments

9.18.4.1 Actigraphy (ActiGraph GT9x)

During the Screening process and prior to baseline assessments, patients will be provided with an ActiGraph GT9x, specific information regarding the device, and the wear protocol. Patients will wear the ActiGraph on their non-dominant wrist throughout the study period (10 hour daytime + full nighttime wear). Daily bouts of activity (energy expenditure) and percent sleep efficiency, nighttime awakenings, and duration of nighttime awakenings will be explored through the ActiLife data analyses software platform. Sleep-wake activity analyses will be performed using R*Studio and nparACT software to compute several non-parametric measures from raw actigraphy data. Specifically, the interdaily stability, intradaily variability, and relative amplitude of activity will be computed to explore sleep-wake activity rhythms (circadian rhythmicity) in study patients.

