12.2 Determination of Sample Size

Assuming a sample size of 20, at least 1 adverse drug reaction with an incidence of 15% may be detected at a probability of $\geq 95\%$ for the safety profile, which is the primary outcome. Based on this, it was decided that 20 patients should be enrolled to confirm safety. A minimum of 8 ambulant patients will be enrolled.

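### Body position/location cannot be derived from per-minute vector magnitude, and the actigraphy validity correlations are not split by ambulatory status

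*Combined protocol and SAP*

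**What the plan says.** Section 12.6.2.5 sets out the device validation: "Validity will be explored through correlation of all clinical strength and function tests and patient reported outcomes with raw data obtained from the AGT9x", with the data for this step limited to those recorded while the clinical tests are being done. The derived quantities follow: "Information such as steps, speed, body position/location (using vector magnitude per minute data) will be derived from the raw data". No algorithm is given for any of them, and nothing is said about reporting by ambulatory status.

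On placement, section 9.18.4.1 says: "Patients will wear the ActiGraph on their non-dominant wrist throughout the study period". That section lists activity bouts (as energy expenditure), sleep measures and circadian rhythm measures. It does not mention steps, speed or position, so it supplies no other derivation for them.

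On the cohort, section 6.1 gives "A target sample size of 20 patients (ambulant and non-ambulant boys" and "a minimum of 8 ambulant patients will be enrolled"; section 12.2 repeats the minimum. Actigraphy is an exploratory endpoint (section 3).

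**The concern.** There are two separate issues.

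The first is a derivation that does not work as stated. Position and location are about direction and place, and the signal named for them keeps neither. A programmer following the text would either produce a variable with no valid meaning or substitute an undocumented method.

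The second is an analysis left open where the choice matters. The validity correlations cover boys who walk and boys who do not. Some of the clinical scales separate these two groups by construction. If device activity also differs between them, a pooled coefficient can be sizeable with no association inside either group, and it could be taken as evidence that the device tracks function. Steps and walking speed also have no stated meaning for a boy who does not walk.

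**Working it through.** **Plan's own figures.** The documents give no power, effect size or SD for actigraphy. The only sample-size figure concerns adverse reactions (section 12.2, 15% incidence, 20 patients). It reproduces: 1 − 0.85^20 = 0.961, which meets the stated 95%. It has no bearing on this point.

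**Step 1: does magnitude carry position?** Vector magnitude is √(x² + y² + z²). For a device at rest under gravity in three orientations:
- (0, 0, 1): √1 = 1.0
- (1, 0, 0): √1 = 1.0
- (0.6, 0, 0.8): √(0.36 + 0.64) = 1.0

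The value is the same each time, because rotating a vector does not change its length. Summarizing by minute cannot restore the lost direction, and the magnitude holds no information on place.

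**Step 2: would axis-level data rescue it?** They would restore direction, but the direction of the non-dominant wrist (section 9.18.4.1). A forearm can be held the same way whether a boy is sitting, standing or lying.

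**Step 3: how many boys may be non-ambulant?** With 20 enrolled and at least 8 ambulant, at most 20 − 8 = 12, or 12/20 = 60%. If final enrollment were 18 or 22, the ceiling would be 10/18 = 55.6% or 14/22 = 63.6%.

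**Step 4: do the clinical scales separate the groups?** Vignos does so by definition: ambulant patients score 1 to 6 and non-ambulant patients 7 to 10 (section 9.16.1.3). On the NSAA, a total of 0 denotes a completely non-ambulant patient (section 9.16.1.5).

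**Step 5: what can pooling alone produce?** Let proportions p and q = 1 − p be ambulant and non-ambulant. Let the group means differ by d within-group SDs on both measures, with zero correlation within each group. The pooled covariance is then pq·d² and each pooled variance is 1 + pq·d², so in absolute value

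r = pq·d² / (1 + pq·d²).

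With p = 8/20 = 0.4, pq = 0.24:

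| d (assumed) | pq·d² | pooled r |
|---|---|---|
| 1 | 0.24 | 0.24/1.24 = 0.19 |
| 2 | 0.96 | 0.96/1.96 = 0.49 |
| 3 | 2.16 | 2.16/3.16 = 0.68 |
| 4 | 3.84 | 3.84/4.84 = 0.79 |

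The result depends mainly on d. At d = 2, a 10:10 split (pq = 0.25) gives 1.00/2.00 = 0.50, and 16 ambulant to 4 non-ambulant (pq = 0.16) gives 0.64/1.64 = 0.39.

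**Step 6: what does splitting cost in precision?** For an observed r of 0.5, the 95% interval by Fisher's z (standard error 1/√(n − 3)) is 0.07 to 0.77 with n = 20, −0.10 to 0.83 with n = 12, and −0.32 to 0.89 with n = 8.

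**The case against.** The strongest reply is that little hangs on this. Actigraphy is exploratory, with no test, alpha or decision attached. Section 12.1 leaves detail to an SAP finalized before database lock, which prevails over the protocol. Silence on stratification is not a commitment to pool. The NSAA was designed for boys who can walk at least 10 meters, and the timed 10-meter test applies to those performing the NSAA (sections 9.16.1.5 and 9.16.1.6), so some restriction to ambulant boys may follow from the tests themselves. The separations in the table are assumed, and nothing in the documents supports a large d for measures such as elbow dynamometry or PARS III. A valid activity measure should also differ between walkers and non-walkers.

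Most of this stands as a limit on size. It justifies the low severity and is why the table starts at 1 SD. It does not rescue position/location: the sentence names a summary of the raw data that lacks the needed information, and no other section offers an alternative. Nor does it answer the stratification point for Vignos, which is scheduled for every boy and cannot overlap between groups. That a device separates walkers from non-walkers is worth showing, but it is a weaker finding than tracking function among boys of like status.

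A reader might infer that steps and speed are also to be taken from per-minute magnitude and so cannot be measured. The documents do not support that. The bracket directly follows body position/location and need not reach back to the other two, and the sentence gives the raw data as their source. The documents contain no figure on how accurately a wrist device measures steps or speed; what they show is only that the derivation, and its meaning in non-walkers, is unspecified.

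**Conclusion.** The derivation of body position/location is wrong as written. This follows from the definition of a magnitude and needs no assumption. The absence of a split by ambulatory status is a gap with a cheap improvement. Its possible effect, a pooled r of 0.19 to 0.79 with no within-group association, rests on assumed separations of 1 to 4 SDs on both measures and on 8 of 20 boys being ambulant. It is an illustration, not a forecast.

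A reader might go further and conclude that the study's activity results as a whole would be misread. That does not follow. Energy-expenditure bouts, interdaily stability, intradaily variability, relative amplitude and sleep scoring do not, as described, use steps, speed or position. What is exposed is the exploratory validity correlations and any step, speed or position summaries. The primary and secondary endpoints are untouched. Severity: minor, worth fixing because it is easy.

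**What to change.** In section 12.6.2.5, or in the SAP before database lock:

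- Use vector magnitude per minute only as a measure of activity volume, for all boys.
- Drop body position/location, or derive wrist orientation from axis-level raw data and report it under that name.
- State the signal and algorithm for steps and for speed, and report both for ambulant boys only.
- Report the validity correlations within ambulant and within non-ambulant boys, as well as pooled, with intervals.

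The cost is wording and programming; the device, data and visits stay the same. The downside is that steps and speed cover fewer boys, possibly only 8, and the within-group correlations are imprecise, as step 6 of the working shows. They should be presented as descriptive.
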